## **Recruitment and Consent Procedures**

Patients who meet the eligibility criteria will be approached by research staff to determine whether they are willing to participate in the study. To eliminate selection bias, any patient who is determined to be a candidate for RARC will be given an option to participate in the study. The inclusion of patients eligible for this study will in no way compromise the quality of health care they will receive. Prior to study entry, the study staff will explain to each potential subject the research objectives, risks and benefits of study participation, alternative treatments available, and the subjects' rights and responsibilities. If the patient agrees to participate, informed consent will be obtained and, after consenting, randomization will take place. Participation in this study will last up to approximately 5 years.

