### Submission and processing of specimens

The cystectomy specimen (with or without uterus, ovaries, or vaginal cuff in females and prostate in males) will be submitted en bloc, processed and assessed in a standardized fashion at all the participating institutions for margin status along with histology, size, stage, grade and presence/absence of lymphovascular invasion. At a minimum the LND will be submitted in two separate packets labeled left and right pelvic. All of these regions may be submitted in smaller packets (e.g. external iliac, obturator, internal iliac) at the surgeons preference. The standardized Cystectomy Pathology Form will be submitted to CRAB.

The perioperative care measures will be performed per institutional standard based on each institution's policy.

**Progression free survival:** From the date of surgery to the date of first documentation of progression or death due to any cause. Patients last known to be alive and progression-free are censored at the date of last contact. Progression will be determined using RECIST 1.1 criteria by the treating physician based on radiographic or pathologic evidence of disease progression, or death from disease. Any documented recurrence will be considered progression. All patients will have been followed for at least 2 years and 65% of patients will have been followed for 3 years.

**Overall survival:** From date of surgery to date of death due to any cause. Patients last known to be alive are censored at the date of last contact.

Serum hemoglobin and a comprehensive metabolic panel (CMP) will be measured on 10 cc of blood obtained by a venipuncture. These laboratory parameters are part of a routine preoperative work up and postoperative follow up in patients undergoing radical cystectomy and urinary diversion. No extra laboratory tests will be administered to the subjects enrolled in this trial.

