**Clinical Procedures**  
Measurements of Study Endpoints

Measurements of the study end points will be conducted according to the following Table 1:

Table 1: Study Calendar

| Assessment  | Baseline
(Preoperative)          | Hospital
Discharge
(±2 weeks) | 4-6
Weeks    | 3
months     | 6
months     | 12
months | 24
Months | 36
Months |
|---|-------------------------------------|-------------------------------------|-----------------|-----------------|-----------------|--------------|--------------|--------------|
| Baseline History and Physical Exam, Consent, Screening, ECOG Performance Status, TURBT findings | √                                   |                                     |                 |                 |                 |              |              |              |
| Randomization   | √ (within 60 days prior to surgery) |                                     |                 |                 |                 |              |              |              |
| Progression Free Survival   |                                     |                                     |                 |                 |                 | √            | √            | √            |
| Overall Survival  |                                     |                                     | √               | √               | √               | √            | √            | √            |
| Activities of Daily Living (ADL) score  | √                                   |                                     | √
(±30 days) | √
(±30 days) | √
(±30 days) |              |              |              |
| Instrumental Activities of Daily Living (IADL) score  | √                                   |                                     | √
(±30 days) | √
(±30 days) | √
(±30 days) |              |              |              |
| Hand Grip Strength Test   | √                                   |                                     | √
(±30 days) | √
(±30 days) | √
(±30 days) |              |              |              |
| Timed Up and Go Walking Test  | √                                   |                                     | √
(±30 days) | √
(±30 days) | √
(±30 days) |              |              |              |
| Hemoglobin, BMP, serum albumin  | √                                   |                                     | √               | √               | √               | √            | √            | √            |

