## Data Submission Procedures

### Data must be submitted according to the following schedule:

- To perform randomization and obtain subject ID number: *Randomization Form.*
  
- Within 1 week following enrollment: All of the following forms:
  - *Medical History Form*
  - *Surgical History Form*
  - *Findings at TURBT Form*
  - *Hemoglobin, BMP, and Serum Albumin Form*
  - *Screening Physical Exam and Vital Signs Form*
  - *Baseline Disease Assessment Form*
  - *Baseline Vanderbilt Cystectomy Index QOL Questionnaire*
  - *Baseline SF-8 QOL Questionnaire*
  - *Baseline Activities of Daily Living QOL Questionnaire*
  - *Baseline Activities of Instrumental Activities of Daily Living QOL Questionnaire*
  - *Baseline Hand Grip Strength Form*
  - *Baseline Timed Up and Go Walking Test Form*
  
- Within 1 week of each post-surgery laboratory assessment per Table 1:
  - *Hemoglobin, BMP, and Serum Albumin Form*
  
- Within 1 week following surgery: *Surgeon's Intra-Op Data Form.*
  
- Within 1 week following discharge for surgical hospitalization:
  - *Hospital Discharge Visit: OR and Hospital Costs Reporting Form*
  - *Surgeon's Post-Op Data Form*
  
- Within 1 week of each scheduled ADL, IADL, and QOL assessment per Table 1:
  - *Vanderbilt Cystectomy Index QOL Questionnaire*
  - *SF-8 QOL Questionnaire*
  - *Activities of Daily Living QOL Questionnaire*
  - *Activities of Instrumental Activities of Daily Living QOL Questionnaire*
  - *Hand Grip Strength Form*
  - *Timed Up and Go Walking Test Form*
  
- Within 2 weeks following each scheduled disease assessment/imaging exam per Table 1: *Post Surgical Disease Assessment Form.*
  
- Within 4-6 weeks post-op: *Cystectomy Pathology Form*
  
- Within 1 week following 90-days post-op: *Surgeon's 90-Day Data Form*
  
- Within 1 week following 6-, 12-, 24-, and 36 months post-op (respectively):

- *Post Surgical Disease Assessment*
  - *Hematology Form*
  - *Serum Chemistry Form*
- Within 1 week following each scheduled adverse events evaluation (per Table 1) until adverse events have resolved. Adverse event information is collected on the *Surgical Complications-Adverse Events Form*.
  - Within the time frame and per the guidelines specified in section 6: *Serious Adverse Events*. Report per the instructions provided in section 6 AND flag as “SAE” on the *Surgical Complications-Adverse Events Form*.
  - Within 2 weeks following knowledge of death, if death occurs prior to end of study: *Death Report Form*.

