Hand Grip Strength at 3 months after surgery will be measured as a surrogate for recovery after surgery. It was found that only 39% of patients recovered at three months after a major abdominal surgery as measured by the Hand Grip Strength. We will compare the proportion of patients recovered as measured by Hand Grip Strength between the two treatment arms. We hypothesize that 20% more patients will have recovered three months after surgery in the RARC arm compared to the ORC arm. A total of 288 patients yield 91% power and a one-sided significance level of 0.025 to detect a difference between arms of at least 20%. These calculations are based on the assumption that Hand Grip Strength at three months is binomially distributed. Surgical margin as a measure for local cancer control will be measured as positive or negative for each patient and compared between arms using a Fisher's exact test. The number of nodes resected in each arm will be compared using a t-test.

Progression-free and overall survival will be evaluated using the method of Kaplan Meyer and comparisons between arms will be made using the stratified log-rank test.

All efficacy and QL endpoints will be assessed using the PP population.

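### Kaplan-Meier PFS and OS curves can be biased downwards after each patient's last scheduled visit, because late deaths count without a time limit while survivors are censored at last contact

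*Combined protocol and SAP*

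**What the plan says.** All references are to the combined protocol and SAP.

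- **Event definitions** (Section 4, Submission and processing of specimens). OS runs "From date of surgery to date of death due to any cause". PFS runs "From the date of surgery to the date of first documentation of progression or death due to any cause". Neither has an upper time limit.
- **Censoring** (same place). For OS, "Patients last known to be alive are censored at the date of last contact". For PFS, "Patients last known to be alive and progression-free are censored at the date of last contact".
- **Scheduled contacts** (Section 4, Table 1 and Data Submission Procedures). The row "Overall Survival" and the PFS row both end at 36 months, as does the form schedule.
- **Death reporting** (Data Submission Procedures). The Death Report Form is due "Within 2 weeks following knowledge of death, if death occurs prior to end of study". The end of study is not defined, and no matching form records that a patient is alive after month 36.
- **Duration.** Recruitment and Consent Procedures says "Participation in this study will last up to approximately 5 years". Section 5, Accrual and Study Duration, gives three years of accrual plus two of follow-up.
- **Completion** (Section 6, Subject Completion and Withdrawal). A subject counts as completed after the 24-month evaluation.
- **Analysis** (Section 5, Secondary Endpoints). "Progression-free and overall survival will be evaluated using the method of Kaplan Meyer", with a stratified log-rank test. No truncation time or data cut-off is given.

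**The concern.** Kaplan-Meier estimation needs the reason for leaving the risk set to be unrelated to the outcome. Under this plan a patient operated on early can have up to about two years between the month-36 visit and study close. A death in that window, once known, is an event at its true date. A patient who lives through the window without further contact is censored back at month 36. Staying in the risk set after the last visit then depends on dying.

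The same happens between months 24 and 36 for the roughly one third of patients whose 36-month visit falls after close, so three-year PFS, listed under Specific Aim 2, is touched as well. At stake are the late parts of the published PFS and OS curves, any median read from them and, to a smaller degree, the three-year estimates.

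**Working it through.** **Inputs from the documents.** About 350 patients accrued over about 36 months; close at month 60; status visits per Table 1, the last at month 36; surgery within 60 days of randomisation; two-year PFS of 71% on open surgery (Power and Significance); drop-out up to 10%.

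**Assumptions.** Uniform accrual, exponential event times, and the same rate in both arms for the curves. The documents give no OS rate, so 75% at two years is assumed where one is needed.

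**The plan's own figures.**
- Sample size: (1.960 + 0.842)² × 2 × 0.71 × 0.29 / 0.15² = 143.7, so 144 per arm and 288 in total, as stated. Nothing after month 24 enters it.
- Share with 36 months of follow-up: (60 − 36)/36 = 66.7%, against the stated 65%.

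**True PFS under the assumptions.** 0.71^(36/24) = 59.8% at month 36 and 0.71^(48/24) = 50.4% at month 48.

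**The risk set just after month 36** (ignoring the delay to surgery). Patients who have reached month 36 before close and are event-free: 350 × 0.667 × 0.598 ≈ 139. In simulation about 22 of them have an event before close and about 118 do not. If none of the 118 is contacted after month 36, the estimator works with 22 patients, all of whom fail, instead of about 139.

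**Simulated Kaplan-Meier PFS.** All events before close are counted. The stated share of event-free patients is contacted at close, and the rest are censored at their last scheduled visit.

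| Survivors contacted at close | Month 24 | Month 36 | Month 48 |
|---|---|---|---|
| 0% | 71% | 57% | 12% |
| 25% | 71% | 58% | 35% |
| 50% | 71% | 59% | 43% |
| 75% | 71% | 59% | 48% |
| 100% | 71% | 60% | 50% |
| True | 71% | 60% | 50% |

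Without the delay to surgery, the 12% becomes 13%.

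**Capture of late events.** The table counts every late PFS event, progression included, whereas the open-ended reporting route is for deaths.
- With no survivor contact this hardly matters: capturing half of the late events still gives about 13% at month 48 (no delay to surgery).
- With partial contact it does matter. If half of late events and half of survivors are captured, 48-month PFS is 50%, with no bias. With half of events and 75% of survivors, it is 54%, which is too high.

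**OS at an assumed 75% two-year rate.** 48-month OS is 13% with no survivor contact and about 49% with half contacted (true 56%). About 18 deaths fall after month 36 and about 7 between months 24 and 36 beyond the last visit, 25 in all.

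**If scheduled contact stopped at month 24.** With no later survivor contact, 36-month PFS is about 27% against 60%.

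**Log-rank test** (unstratified, OS at an assumed 80%, equal capture in both arms). Two-sided type I error is 4.4% with no survivor contact and 5.2% with full contact. Power at an illustrative hazard ratio of 1.6 is 66% and 78% respectively; part of that gap is simply lost follow-up.

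**The case against.** The strongest reply is that the documents do not fix how survivors are followed after their last visit. The censoring rule refers to the last contact, not the last scheduled visit. Participation may last about five years. Adverse events are followed until they resolve. Death reporting is itself passive, so whatever brings a death to light could equally show that a patient is alive. End of study might also mean the subject's own end, in which case later deaths would not be reported at all. Equal capture gives no bias, and poorer capture of deaths than of survivors gives a curve that is too high.

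This stands as a limit on certainty and size. A reader might infer that the curves must collapse towards zero after month 36. The documents do not support that: it needs no survivor contact at all after the last visit, and with half of survivors contacted the 48-month error is about 7 points rather than 38.

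It is also true that OS is absent from the objectives in Section 3, and that no median or 48-month estimate is named as an endpoint. But the plan applies Kaplan-Meier to both outcomes with no stopping time, so the tail will be estimated.

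The reply does not remove the point. The bias is absent only when survivors and late events are captured equally, and nothing in the plan secures that. A form exists for a death after month 36 and none for being alive.

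**Conclusion.** The concern holds as a conditional one. Followed exactly as scheduled, the plan gives late PFS and OS curves that are too low; with partial survivor contact and full capture of events, the bias shrinks but remains. At 71% two-year PFS with exponential times, 48-month PFS is about 12%, 43% or 48% with 0%, 50% or 75% of survivors contacted (true 50%). Three-year PFS is low by up to about 3 points if the month-36 visits take place.

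Two stronger readings should be set aside. The primary two-year comparison is not affected: the month-24 estimate is 71% in every scenario and the 288 is unchanged. Nor is the log-rank test shown to be invalid: its type I error stays near 5% when capture is the same in both arms.

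The conflict between completion at month 24 (Section 6) and a calendar to month 36 (Table 1) could make matters worse. If scheduled contact stopped at month 24, the false fall could start there and three-year PFS could be badly wrong. The OS figures rest on an assumed rate.

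**What to change.** Define the end of study and one data cut-off date, and reconcile the completion rule in Section 6 with Table 1. Then add one of the following to the PFS and OS definitions in Section 4 and to Secondary Endpoints in Section 5.

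1. **Cap.** *For Kaplan-Meier and log-rank analyses, follow-up is capped at the last scheduled status visit due before the data cut-off, and at most at 36 months after surgery. Events after the cap are not counted. Event-free patients are censored at the earlier of their actual last contact and the cap.* The last clause matters: censoring at the visit due date alone would treat patients lost early as event-free to month 24 or 36. With 10% drop-out spread evenly over 24 months, that gives a three-year PFS of 62.3% against a true 59.8%, whereas the wording above gives 59.8%.
2. **Status update.** *Vital and disease status is updated for all patients at the data cut-off, and survivors are censored at their last confirmed status.* In simulation, full updating restores 48-month PFS to 50%.

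The cap costs one or two sentences and no extra visits, but leaves about 25 late deaths out of the OS curves (at 75% two-year OS). In a simulation with a hazard ratio of 1.5, log-rank power was 62.9% with truncation at the last scheduled contact and 60.5% without it. The status update keeps the late deaths, at the price of one contact round across about 15 sites.

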##### Specific Aim 2 :

1. Serum Hemoglobin, Serum Creatinine and Serum Albumin levels at baseline and in the post operative period at 4-6 weeks, 3 months, 6 months, 12 months, 24 months, and 36 months.
2. Quality of Life (QOL) outcomes at baseline and in the post operative period at 3 months and 6 months using the Functional Assessment of Cancer Therapy - Vanderbilt Cystectomy Index (FACT-VCI) as well as the Short Form 8 (SF-8) Questionnaires.

3. Compare surrogates of surgical quality by evaluating surgical margin status and number of lymph nodes harvested.
4. Compare surgical morbidity by evaluating complication rates at 90 days post operative using the modified Clavien grading system.
5. Perioperative measures such as Estimated Blood Loss (EBL), Blood transfusion rates, total intraoperative fluid requirements, total operative time, total postoperative length of hospital stay and analgesic requirement.
6. *3 year progression free survival in 65% of patients.*

Specific Aim 3 :

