Pathologic data will be obtained from the pathology reports after surgery with particular emphasis on the involvement of surgical margins with cancer, total number of lymph nodes harvested and their involvement with cancer as well as the pathologic stage of the tumor. All institutions will adopt a standardized procedure to process the cystectomy specimens along with the lymph nodes. A standardized form will be used to collect all the information pertaining to specimen processing and staging by the participating institutions. A copy of the pathologic form will be available in the patients' clinical records.

Perioperative mortality and morbidity will be evaluated using the modified Clavien grading system for complications by prospectively recording the intraoperative and post operative complications until discharge and by patient interview during post discharge period until 4-6 weeks after surgery. The above data will be separately recorded in the patient's clinical records in an inpatient and outpatient setting.

Perioperative measures such as estimated blood loss (EBL), blood transfusion rates, total intraoperative fluid requirements, total operative time, total postoperative length of hospital stay and analgesic requirement will be prospectively recorded during the surgery and the postoperative hospital stay using the anesthesia, operative, nursing and inpatient medical records by a research coordinator. All medications will be converted to morphine equivalents by using the online calculator The Clinician's Ultimate Reference found at <http://www.globalrph.com/narcoticonv.htm>

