|  |   |         |   |                 |                 |   |   |   |
|--|---|---------|---|-----------------|-----------------|---|---|---|
| Quality of Life Questionnaire (QOL) - Vanderbilt Cystectomy Index and SF8  | √ |         |   | √
(±30 days) | √
(±30 days) |   |   |   |
| Obtain Pathology Reports for Surgical Margin Status and Lymph Node Count   |   |         | √ |                 |                 |   |   |   |
| Surgical Complications per Modified Clavien Classification (AEs)/ Serious Adverse Events   |   |         | √ | √               | √               | √ | √ | √ |
| Postoperative Complication Rates (Surgeon's 90-Day Data Form)  |   |         |   | √               |                 |   |   |   |
| Imaging (CT scan /MRI /Xray/etc of Abdomen/Pelvis/Chest /etc)  | √ |         |   |                 |                 | √ | √ | √ |
| OR Costs
Hospital Costs   |   | √       |   |                 |                 |   |   |   |
| Surgeon's Intra Op Data, Cystectomy Pathology  |   | Post Op |   |                 |                 |   |   |   |
| Length of Hospital Stay, Analgesics, Complications (Surgeon's Post Op Data Form)   |   | √       |   |                 |                 |   |   |   |
| Target Lesions (Post Surgical Disease Assessment Form) to document cancer progression, according to local site Standard of Care. |   |         |   |                 | √               | √ | √ | √ |

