### **Special Precautions**

Subject data will be examined at each follow up visit and subjects queried for adverse events (AE) defined as complications related to the robotic/open cystectomy and/or study procedures. An AE or complication is the appearance of undesirable sign(s), symptom(s), or medical condition(s) occurring after a participant signs the informed consent and considered to be related to the robotic/open cystectomy and/or study procedure. A serious adverse event is any untoward medical occurrence that:

1. Is fatal or life-threatening
2. Requires hospitalization or prolongation of existing hospitalization
3. Results in disability/incapacity
4. Is medically significant in that it may jeopardize the patient and may require medical or surgical intervention to prevent one of the outcomes listed above.

All AEs or complications will be graded for severity according to the modified Clavien grading system. All adverse events will be reported to the IRB at the time of annual review and to the DSMC as described below.

The investigator is obligated to assess the relationship between any study-related procedure and the occurrence of each SAE. The investigator will use clinical judgment to determine the relationship. Alternative causes, such as natural history of the underlying diseases, concomitant therapy, other risk factors, and the temporal

relationship of the event to any study-related procedure will be considered and investigated.

Even in situations when an SAE has occurred and the investigator has incomplete information to include in the initial SAE report, the investigator will make an assessment of causality for every event prior to reporting it. The investigator may change his opinion of causality in light of follow-up information and amend the SAE case report form and report accordingly.

SAEs meeting the IRB definition of Unanticipated Problems Involving Risk to Subjects or others (UPIRSO) will be reported to the IRB within 7 days, and within 48 hours if life-threatening or fatal or will follow the guidelines as required by the local IRBs.

All SAEs will also be reported to the coordinating center office of [name] at the University of Miami. After completion of review by [name], SAEs will be summarized and communicated across sites via the posting to the study website at <https://prodq.crab.org/[name]/Login.aspx>.

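### Whether a 90-day complication counts depends on a judgment that it is related to surgery, with no blinding or independent adjudication described; the 4-6-week interview wording also needs aligning with day 90

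*Combined protocol and SAP*

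**What the plan says.** **Endpoint.** Section 3, Specific Aim 2, item 4: "Compare surgical morbidity by evaluating complication rates at 90 days post operative using the modified Clavien grading system".

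**What counts.** Section 6, Special Precautions, gives one definition for an adverse event or complication. The event must arise after consent and be "considered to be related to the robotic/open cystectomy and/or study procedure". The same section then applies the modified Clavien grading to all adverse events or complications, that is, to the events that passed this condition. The serious adverse event definition beside it covers any untoward event meeting one of four seriousness criteria. Relatedness is not part of that definition; the investigator assesses it afterwards by clinical judgment. Under Data Submission Procedures, both kinds of event go on the Surgical Complications-Adverse Events Form.

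**When it is collected.** Section 4, under the heading on submission and processing of specimens, says that perioperative morbidity is recorded until discharge and then "by patient interview during post discharge period until 4-6 weeks after surgery". Three other places carry collection further:

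- Table 1 has a row for "Surgical Complications per Modified Clavien Classification (AEs)/ Serious Adverse Events", ticked at 4-6 weeks and at 3, 6, 12, 24 and 36 months, and a separate row for the Surgeon's 90-Day Data Form, ticked at 3 months.
- Data Submission Procedures makes that form due "Within 1 week following 90-days post-op".
- Special Precautions has subjects asked about adverse events at each follow-up visit.

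**What is not said.** The documents describe no blinding of patients, surgeons or assessors and no independent adjudication of complications. Section 5 names no test for the 90-day complication rate.

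**The concern.** In a comparison of two operations, a rule that only related events are complications puts a causal judgment ahead of the count. If the person judging knows which operation was done, the threshold for calling an event related can differ by arm without anyone intending it. Section 2 states an expectation that RARC might reduce complication rates, so the judgment would not be made in a neutral setting. The bias could still run either way.

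The two definitions in Special Precautions make this worse. On a plain reading, a serious event can reach the form whatever its cause, while a non-serious event reaches it only after being judged related. What counts as a complication is then unsettled, and the filter acts mainly on the common lower-grade events.

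At stake is a named between-arm comparison of surgical morbidity. The primary test of two-year progression-free survival is not affected.

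**Working it through.** The plan gives no sample size, power or effect size for complications, so it has no figure of its own to reproduce. The check has two parts.

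**1. Effect of attribution that differs by arm**

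Inputs from the documents:

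- Reported complication rates after open surgery: about 67% minor and 13% major (section 2).
- Evaluable patients: 144 per arm (section 5, Power and Significance).

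Assumptions, because the documents give no capture rates:

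- The true rate p is the same in both arms.
- A fraction L of affected patients is lost from the count in one arm only, with L = 5% or 10%.
- The test is a two-sided 5% pooled two-proportion z-test.

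False difference: d = p × L.

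Rejection probability: 1 − Φ((1.96·s0 − d)/s1) + Φ((−1.96·s0 − d)/s1), where

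- s0 = √(2·p̄(1 − p̄)/144), with p̄ the mean of the two observed rates;
- s1 = √((p1(1 − p1) + p2(1 − p2))/144).

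Worked case, p = 0.67 and L = 10%: p1 = 0.670, p2 = 0.603, d = 0.067, p̄ = 0.6365, s0 = 0.0567, s1 = 0.0565. The rejection probability is 0.219.

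| True rate, both arms | Lost in one arm only | Counted rates | False difference | Rejection probability |
|---|---|---|---|---|
| 67% | 5% | 67.0% v 63.65% | 3.35 points | 9% |
| 67% | 10% | 67.0% v 60.3% | 6.7 points | 22% |
| 13% | 5% | 13.0% v 12.35% | 0.65 points | 5% |
| 13% | 10% | 13.0% v 11.7% | 1.3 points | 6% |

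With equal loss of 20% in both arms at p = 0.67, the counted rates are 53.6% v 53.6% and the rejection probability stays at 5%. Only unequal loss creates a false difference.

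L is a share of affected *patients*. If 10% of *events* were discounted, fewer than 10% of affected patients would drop out of the count, because a patient with two events still counts if one is kept. Read that way, the table gives upper bounds.

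**2. The window**

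The interview text ends at day 28 to 42, which is 90 − 42 = 48 to 90 − 28 = 62 days before day 90. Set beside it, the 3-month visit has a Clavien tick in Table 1, subjects are asked about adverse events at every follow-up visit, and the 90-day form is due just after day 90. Power and Significance also makes 90-day follow-up data part of being evaluable. The interview sentence is therefore out of step with the rest of the plan, but the endpoint has a collection route to day 90.

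**The case against.** **On the window.** A reader might infer from the interview sentence that 48 of the 90 days (48/90 = 53%) have no patient contact, or rest on the surgeon's form alone, and that this under-counts unequally by arm. The documents do not support that. Section 4 says that endpoints are measured according to Table 1, which carries Clavien collection to 3 months and beyond, and Special Precautions has patients asked at each visit. Any cut-off would also apply identically to both arms, and part 1 of the check shows that equal loss with equal true rates gives no false difference. The objection stands in full on this limb; only the wording mismatch is left.

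**On relatedness.** The case against is partly right:

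- Lack of blinding is inferred from silence.
- The assessor of relatedness is named only for serious events.
- No passage says that the 90-day form applies the filter, which sits in the human-subjects section.
- The definition is worded the same way for both operations.

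These points limit the certainty but do not remove the concern. The definition uses the word complication itself, and the Clavien grading in that section is applied to the set it defines. A surgeon who operated and then completes the 90-day form necessarily knows the arm. Identical wording does not ensure identical judgment. Whether the form applies the filter is itself something the plan should settle.

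**On size and remedy.** The loss fractions are assumed, and the effect at the major-complication rate is small. Counting all causes brings in events unrelated to surgery, which can dilute a real difference, and it leaves site staff deciding what to report and how to grade it. All of this stands.

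**Conclusion.** The concern holds for the relatedness condition. As written, a between-arm comparison named in Specific Aim 2 can depend on attribution by staff who know the arm, with no blinding or adjudication described, and serious and non-serious events enter under different rules. This is a possible route to bias; nothing in the documents shows that bias occurs.

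Its size cannot be estimated from the documents. Under the stated assumptions, a one-sided loss of 5-10% of affected patients gives a false difference of about 3 to 7 points at a 67% rate, with a false-positive rate of 9% to 22% in place of 5%. At a 13% rate the difference is about 1 point and the false-positive rate barely moves. The exposure lies with common lower-grade complications.

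The interview wording is a separate and smaller matter: an inconsistency to reconcile that affects both arms alike. The change is worth making because it is cheap. It alters no sample size.

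**What to change.** 1. In Specific Aim 2 and Special Precautions, define the 90-day complication endpoint as all modified-Clavien-graded events from surgery to day 90, regardless of attribution. State that the Surgeon's 90-Day Data Form and the Surgical Complications-Adverse Events Form both follow this rule.
2. Record relatedness as a separate field on the existing complication form. A related-only count can then be a supporting analysis, and attribution stays available for safety reporting.
3. In section 4, extend the interview wording to day 90 so that it agrees with Specific Aim 2, Table 1 and Special Precautions.

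Cost: changes of wording, one field, and somewhat more events to enter, using visits and forms that already exist. All-cause counting brings some dilution from events unrelated to surgery. It does not remove arm-aware reporting or grading; masked grading would be needed for the grading part and is a further option at extra cost.
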